4. STUDY OBJECTIVES AND ENDPOINTS

The aim of this non-interventional study is to evaluate the overall effectiveness and safety of Roctavian compared to SoC hemostatic prophylaxis treatments for PwSHA.

The specific objectives are listed below. All objectives will compare Roctavian and SoC with exogenous FVIII or emicizumab, unless otherwise noted.

Table 1: Objectives and Endpoints

[figure not shown]
Objectives	Endpoints
Primary	
To compare the annualized bleeding rate for treated bleeds.	
 Bleeding events requiring treatment with exogenous FVIII
Secondary	
To compare the annualized bleeding rate for major, life threatening, and joint bleeds.	
 Major bleeding events Life-threatening bleeding events Bleeding events occurring in the joint
To compare the proportion of people with zero bleeds for treated, major, life threatening, and joint bleeds.	
 Bleeding events requiring treatment with exogenous FVIII Major bleeding events Life-threatening bleeding events Bleeding events occurring in the joint
To compare the use of hemostatic medications.	
 Prophylactic hemostatic treatments On-demand hemostatic treatments
To compare joint health, quality of life, and pain.	
 Hemophilia Quality of Life assessment (Haemo-QoL-A) Hemophilia Joint Health Score (HJHS) Brief Pain Inventory-Short Form (BPI-SF)
To compare safety events of interest.	
 All cause death Hemophilia-related death Adverse events leading to hospitalization or death Targeted adverse events of development of FVIII inhibitors, thromboembolic events, new malignant neoplasms, and severe liver disease (liver failure or cirrhosis)
To describe time to resumption of prophylactic treatment among persons administered Roctavian.	
 Resumption of prophylactic hemostatic treatments

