7.2.5.7. Safety outcomes

Safety events of interest (all cause death, hemophilia-related death, adverse events leading to hospitalization and/or death, and targeted adverse events of development of FVIII inhibitors, thromboembolic events, new malignant neoplasms, and severe liver disease) will be described for each cohort based on data recorded in the DHR. See [Table 8](#) for detail on events captured and relevant data field when applicable. Safety events will be described and compared based on events recorded starting on the index date and throughout the follow-up period for each participant.

Refer to [Section 9](#) for additional information on safety reporting expectations.

Table 8: Safety Events of Interest

Variable	Description	Captured in DHR	Time period for Analysis	Entry into DHR	Operational notes including Relevant Data Fields in DHR
All cause death	Deaths occurring due to any cause	✓	Follow-up (inclusive of index)	Ongoing	Derived based information entered into the DHR when a participant is no longer enrolled in the DHR due to the reason being death and cause of death identified as hemophilia-related, non-hemophilia-related, or unknown. (See limitations of interpretation of events regardless of relationship to hemophilia treatment in Section 10.5).
Hemophilia-related death	Deaths occurring due to the disease	✓	Follow-up (inclusive of index)	Ongoing	Derived based information entered into the DHR when a participant is no longer enrolled in the DHR due to the reason being death and cause of death identified as hemophilia-related.

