Adverse events leading to hospitalization and/or death	Medical event leading to hospitalization and/or death	✓	Follow-up (inclusive of index)	Ongoing	
The DHR captures information on medically relevant events including allergic reactions, thromboembolic events, thrombotic microangiopathy, malignant neoplasm, autoimmune disease, sensory paresthesia, infusion/hypersensitivity reaction, complications of immunosuppression and other with a free text field to specify the other category. For each event, the connection to hemophilia treatment (yes/no/unknown) is also recorded, along with serious consequences due to the event (hospitalization, death, none or unknown).
 
Event recorded as leading to hospitalization and/or death will be analyzed both for any reason (regardless of relation to hemophilia treatment) and related to hemophilia treatment. (See limitations of interpretation of events regardless of relationship to hemophilia treatment in Section 10.5).
 
Hospitalizations are defined as a participant having been admitted to the hospital for inpatient care, either to the inpatient ward or to the emergency room for observation and/or treatment that would not have been appropriate in the physician’s office or outpatient setting.

Variable	Description	Captured in DHR	Time period for Analysis	Entry into DHR	Operational notes including Relevant Data Fields in DHR
Targeted Adverse Events					
Development of FVIII inhibitors	Positive inhibitor tests and/or a positive test and the requirement for ITT	✓	Follow-up (inclusive of index)	Ongoing	Based on recording of the DHR variables for positive inhibitor tests after enrollment in the DHR, or use of immune tolerant therapy (ITT). See Table 4 and SAP for additional information on definition for positive inhibitors based on 2 positive tests or 1 test and use of ITT.
Thromboembolic events	Occurrence of a thromboembolic event related to treatment	✓	Follow-up (inclusive of index)	Ongoing	Derived based recording of medically relevant event of thromboembolic event in the DHR that has been identified as connected to hemophilia treatment. Occurrence of thromboembolic events regardless of relationship to treatment will also be described, but not compared. (See limitations of interpretation of events regardless of relationship to hemophilia treatment in Section 10.5)

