Malignant neoplasms	Occurrence of a malignancy	✓	Follow-up (inclusive of index)	Ongoing	Derived based recording of medically relevant event of malignant neoplasm in the DHR. Malignant neoplasms have cells that grow uncontrollably and spread locally and/or to distant sites. Malignant tumors are cancerous (ie, they invade other sites). They spread to distant sites via the bloodstream or the lymphatic system. This spread is called metastasis. Metastasis can occur anywhere in the body (Patel 2020). Malignancies are expected to be defined consistent with other data collection occurring in the study population, including the International World Federation of Hemophilia Gene Therapy Registry (WFH 2024 ; Konkle 2020).
Severe liver disease (liver failure, liver fibrosis and/or progression of liver)	Occurrence of new severe liver disease	✓	Follow-up (inclusive of index)	Ongoing	Derived based on recording of liver disease status (liver fibrosis (new diagnosis), liver failure, and liver cirrhosis). Occurrence of severe liver disease (liver failure, liver fibrosis and/or progression of liver fibrosis, or cirrhosis). Recording during follow-up of ‘liver fibrosis (new diagnosis)’ or ‘liver failure’ will be used to identify events. Progression of fibrosis or cirrhosis will be identified based on recording of an increased Child-Turcotte-Pugh classification (eg, A → B, B→C) of liver disease relative to liver disease status at baseline or the new diagnosis of cirrhosis (Lee 2022 ; Lee 2022a ; Tholey 2023). Definitions of acute liver failure

Variable	Description	Captured in DHR	Time period for Analysis	Entry into DHR	Operational notes including Relevant Data Fields in DHR
fibrosis, or cirrhosis)					
(Tholey 2023), liver fibrosis and/or progression of liver fibrosis (Lee 2022a), or cirrhosis (Lee 2022) will be consistent with MSD Manuals for classification.
 
Similar to the description of thromboembolic events, both events regardless of relationship to hemophilia treatment and specifically related to hemophilia treatment will be analyzed. (See limitations of interpretation of events regardless of relationship to hemophilia treatment in Section 10.5).
 
The definition of severe liver disease (acute liver failure, worsening of liver fibrosis, liver cirrhosis) is consistent with other data collection occurring in the study population, including the International World Federation of Hemophilia Gene Therapy Registry (WFH 2024; Konkle 2020).

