Descriptive statistics will be used to summarize the absolute and change from baseline at the time of an assessment for the total and domain scores for the Haemo-QoL-A and the BPI-SF. For the BPI-SF the pain interference and pain intensity scores will be taken as the domains. A repeated measurement analysis model will be used to compare the changes in scores between the treatment groups. Participants with an evaluable baseline score and at least one evaluable post-baseline score will be required for the specific analysis be included in the change from baseline analyses.

In addition, responder analyses will be considered for improvement and deterioration for the BPI-SF pain interference and pain intensity scales. The BPI-SF pain intensity score will be defined as the Question 5 “average pain”. The BPI-SF pain interference score will be defined as the average to all 7 subitems of Question 9 (9A to 9G).

All analysis details and scoring methods will be described in the SAP. It is expected that no missing data will be imputed.

All PROs comparisons will be interpreted after 3 years of follow-up, or latest available follow-up score if a full 3 years of follow-up is not available.

10.3.7.5. Objective: To compare safety events of interest.

Safety events outlined in [Table 8](#) will be described in each cohort. Summaries of the proportion, event rate, and incidence rate of each of the safety events among all participants by cohort will be provided. Safety events will be described from index through follow-up. All participants will be included in analyses of event and incidence rates, while analyses of the proportion of participants will only include those participants with follow-up for the full time over which the proportion is calculated. Safety outcomes will be compared as relative risks based on the incidence of an event for analyses of the treatment policy estimand and as incidence rate ratios censoring a participants person time at the time of the event for analyses of the hypothetical estimand.

10.3.7.6. Objective: To describe time to resumption of prophylactic treatment among participants administered Roctavian

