Malignant neoplasms	Yes	
 Other relevant event Relation to hemophilia treatment 	
 Derived based on recording of medically relevant event of malignant neoplasm in the DHR³ Malignant neoplasms connected to hemophilia treatment will be identified if other relevant event = “neoplasm” and relation to hemophilia treatment = “yes” Occurrence of malignant neoplasm regardless of relationship to treatment will also be described, but not compared Malignancies are expected to be defined consistent with other data collection occurring in the study population, including the World Federation of Hemophilia Gene Therapy Registry^{20, 21} 	All available follow-up
Severe liver disease	Yes	
 Liver disease status Date of liver fibrosis (new diagnosis) Relation to hemophilia treatment 	
 Derived based on recording of liver disease status (liver fibrosis [new diagnosis], liver failure, and liver cirrhosis) 
 Recording during follow-up of “liver fibrosis (new diagnosis)” or “liver failure” will be used to identify events Progression of fibrosis or cirrhosis will be identified based on recording of an increased grade of liver fibrosis/cirrhosis relative to liver disease status at baseline Severe liver disease connected to hemophilia treatment will be identified if relation to hemophilia treatment = “yes” Both events regardless of relationship to hemophilia treatment and specifically related to hemophilia treatment will be analyzed Progression of fibrosis or cirrhosis will be identified based on recording of an increased Child-Turcotte-Pugh classification (e.g., A → B, B → C) of liver disease relative to liver disease status at baseline or the new diagnosis of cirrhosis¹⁷⁻¹⁹ The definition of severe liver disease is consistent with other data collection occurring in the study population, including the international World Federation of Hemophilia Gene Therapy Registry^{20, 22} 	All available follow-up

Variable	Captured in DHR	DHR data field name(s)	Operational definition and calculation of outcome measures	Timepoints for data collection
			
 Definitions of acute liver failure, liver fibrosis and/or progression of liver fibrosis, or cirrhosis will be consistent with MSD Manuals of classification¹⁷⁻¹⁹ 	

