AEs leading to death – connected to hemophilia treatment	0	0.0%	0	0.0%	0.0000	0.00	0	0.0%	0	0.0%	0.0000	0.00
Development of FVIII inhibitors	0	0.0%	0	0.0%	0.0000	0.00	0	0.0%	0	0.0%	0.0000	0.00
Thromboembolic events – any cause	0	0.0%	0	0.0%	0.0000	0.00	0	0.0%	0	0.0%	0.0000	0.00
Thromboembolic events – connected to hemophilia treatment	0	0.0%	0	0.0%	0.0000	0.00	0	0.0%	0	0.0%	0.0000	0.00
Malignant neoplasms	0	0.0%	0	0.0%	0.0000	0.00	0	0.0%	0	0.0%	0.0000	0.00
Severe liver disease – any cause	0	0.0%	0	0.0%	0.0000	0.00	0	0.0%	0	0.0%	0.0000	0.00
Severe liver disease – connected to hemophilia treatment	0	0.0%	0	0.0%	0.0000	0.00	0	0.0%	0	0.0%	0.0000	0.00

Data source: DHR from the start of data collection accompanying the application to approximately 6 months prior to the date of the final report required by the G-BA resolution for AbD

Acronyms: SoC: standard of care; AE: adverse event; FVIII: coagulation factor VIII

Note: Std. diff. examines the balance of covariate distribution between groups, with a value >0.1 indicating some imbalance between groups and >0.25 indicating poor balance.

Table 16 Safety Outcomes for Roctavian and SoC Cohorts

Unadjusted Regression Model

Measures	Regression coefficient	95% Confidence Limits		r ²	p-value
		Lower Limit	Upper Limit		
All cause death	0.00	0.00	0.00	0.00	0.0000
Hemophilia-related death	0.00	0.00	0.00	0.00	0.0000
AEs leading to hospitalization – any cause	0.00	0.00	0.00	0.00	0.0000
AEs leading to hospitalization- connected to hemophilia treatment	0.00	0.00	0.00	0.00	0.0000
Development of FVIII inhibitors	0.00	0.00	0.00	0.00	0.0000
Thromboembolic events – any cause	0.00	0.00	0.00	0.00	0.0000
Thromboembolic events – connected to hemophilia treatment	0.00	0.00	0.00	0.00	0.0000
Malignant neoplasms	0.00	0.00	0.00	0.00	0.0000
Severe liver disease – any cause	0.00	0.00	0.00	0.00	0.0000
Severe liver disease – connected to hemophilia treatment	0.00	0.00	0.00	0.00	0.0000

IPTW-Adjusted Regression Model

Measures	Regression coefficient	95% Confidence Limits		r ²	p-value
		Lower Limit	Upper Limit		
All cause death	0.00	0.00	0.00	0.00	0.0000
Hemophilia-related death	0.00	0.00	0.00	0.00	0.0000
AEs leading to hospitalization – any cause	0.00	0.00	0.00	0.00	0.0000
AEs leading to hospitalization- connected to hemophilia treatment	0.00	0.00	0.00	0.00	0.0000
Development of FVIII inhibitors	0.00	0.00	0.00	0.00	0.0000
Thromboembolic events – any cause	0.00	0.00	0.00	0.00	0.0000

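### The protocol, SAP text and table shells disagree on whether all new malignancies, and any-cause thromboembolic events, are compared or only those the physician marks as treatment-related

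*Protocol*

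**What the plan says.** **Malignancy, protocol.** Section 4, Table 1 sets the objective "To compare safety events of interest", and its targeted events include "new malignant neoplasms, and severe liver disease (liver failure or cirrhosis"). Section 7.2.5.7 adds: "Safety events will be described and compared based on events recorded starting on the index date". The Table 8 malignancy row reads "Derived based recording of medically relevant event of malignant neoplasm in the DHR" and sets no condition on relatedness. Section 10.3.7.5 gives the measure: "Safety outcomes will be compared as relative risks based on the incidence of an event for analyses of the treatment policy estimand", with incidence rate ratios under the hypothetical estimand.

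**Malignancy, SAP.** The malignancy row of Table 5 (section 7.4.3) opens with the same unfiltered derivation. It then defines a subset by event value neoplasm and a relation-to-treatment field equal to yes, and adds "Occurrence of malignant neoplasm regardless of relationship to treatment will also be described, but not compared". Shell Tables 15 and 16 (section 12.1) have a single malignancy row with p-values and regression estimates, unadjusted and IPTW-adjusted. There is no separate treatment-connected row.

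**Thromboembolic events.** Protocol Table 8 counts events connected to hemophilia treatment and adds "Occurrence of thromboembolic events regardless of relationship to treatment will also be described, but not compared". SAP Table 5 uses the same related-only definition. Shell Tables 15 and 16 nevertheless have a row "Thromboembolic events – any cause", with p-values and estimates, beside the treatment-connected row.

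**Other safety outcomes.** All-cause death and FVIII inhibitors carry no relatedness condition. Adverse events leading to hospitalization or death, and severe liver disease, are analysed both for any cause and as related.

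**The concern.** Three parts of the plan specify the malignancy comparison and do not agree. An analyst who follows protocol Table 8 compares every new malignancy. One who follows the SAP sentence compares only those marked related. One who fills the shells has a single tested row and no instruction on which events go in it.

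The choice matters because relatedness is a yes/no/unknown entry made by a physician who knows the treatment, and the plan describes no adjudication. Keeping only yes also drops the unknown entries, and SAP section 7.9.4.5 expects some unknown responses. If physicians attribute tumours differently after a gene therapy than under FVIII or emicizumab, the cohorts are counted by different rules. IPTW does not repair that, because it balances baseline covariates and not the way outcomes are classified.

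For thromboembolic events the issue is narrower. The written rule is the same in both texts, but the shells test something that the protocol says is not compared.

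**Working it through.** **Step 1: set the sources side by side.**

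| Event | Protocol Table 8 | SAP Table 5 | Shell Tables 15 and 16 |
|---|---|---|---|
| Malignant neoplasm | any recorded; compared | related subset defined; all-cause not compared | one undivided row, tested |
| Thromboembolic event | related only compared; all-cause described | related only | any-cause and related rows, both tested |
| Severe liver disease | both analysed | both analysed | both rows, tested |

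For malignancy, the SAP text conflicts with the protocol and sits uneasily with its own shells. For thromboembolic events, protocol and SAP definitions match, and the mismatch is with the shells.

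**Step 2: what a related-only comparison estimates.** Let λ be the true event rate and a the share of events called related, with subscripts R (Roctavian) and S (SoC). The rate of compared events in a cohort is λ × a, so

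apparent ratio = (λ_R / λ_S) × (a_R / a_S).

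The documents give neither share. The values below are assumptions, with true ratio 1:

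| a_R | a_S = 5% | a_S = 10% | a_S = 30% |
|---|---|---|---|
| 10% | 2 | 1 | 0.33 |
| 30% | 6 | 3 | 1 |
| 50% | 10 | 5 | 1.67 |
| 80% | 16 | 8 | 2.67 |

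The extremes are 0.10/0.30 = 0.33 and 0.80/0.05 = 16. The ratio is undistorted only where the shares are equal.

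**Step 3: how few events are involved.** Take the target cohorts (70 and 330) and full 3-year follow-up: 70 × 3 = 210 and 330 × 3 = 990 person-years. Malignancy incidence is not given, so assume 2, 5 or 10 per 1,000 person-years in both cohorts.

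| Rate per 1,000 | All-cause, Roctavian | All-cause, SoC | Related at 50% of Roctavian | Related at 5% of SoC |
|---|---|---|---|---|
| 2 | 0.42 | 1.98 | 0.21 | 0.10 |
| 5 | 1.05 | 4.95 | 0.53 | 0.25 |
| 10 | 2.10 | 9.90 | 1.05 | 0.50 |

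**Step 4: the opposite failure.** Suppose Roctavian truly doubles a rate of 5 per 1,000 and 5% of events are called related in both cohorts. Expected compared events are 210 × 0.010 × 0.05 + 990 × 0.005 × 0.05 = 0.105 + 0.2475 = 0.3525. Under a Poisson count, the chance that no event is compared is exp(−0.3525) = 0.70. At base rates of 2 and 10 per 1,000 the expected totals are 0.141 and 0.705, and the chance is 0.87 and 0.49.

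**The case against.** The strongest reply is that the SAP does not clearly adopt an attribution gate. Its malignancy row starts from the unfiltered derivation, and the shells test malignancies in one undivided row. The sentence about describing without comparing appears in the protocol's thromboembolic row. It is absent from the SAP's thromboembolic row and turns up in the malignancy row directly below. That looks like a drafting slip, although this is inference, and protocol section 10.3 calls the SAP a draft still to be finalised. The reply stands as far as it goes: the defect is an unresolved contradiction, not a proven deliberate choice. The contradiction still has to be removed.

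Protocol section 10.5 also gives a reason for caution: all-cause comparisons of rare events can mislead, for example if one cohort is older. That is fair. But age and cancer history are candidate propensity score variables (protocol Table 9), the safety models are IPTW-weighted, and the same caution did not stop the plan from comparing all-cause death or analysing any-cause severe liver disease.

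Nor would the all-cause comparison be precise, with about 1 against 5 events at the middle assumed rate. The SAP foresees this with a Firth-type correction for sparse events, and secondary p-values are nominal. The case for the change is that the endpoint is defined alike in both cohorts, not that power is gained.

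Two stronger readings are tempting. A reader might infer that thromboembolic events show the same protocol-versus-SAP conflict; they do not, since both texts use related events only. A reader might also infer that attribution governs the whole safety comparison. It does not: all-cause death, inhibitors, any-cause hospitalization or death events and any-cause severe liver disease remain. Malignancies and thromboembolic events that lead to hospitalization or death already enter that any-cause analysis.

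**Conclusion.** The concern holds in a limited form. For malignancy, the SAP sentence contradicts the protocol's objective and Table 8, and the shells do not settle which rule applies. For thromboembolic events, the texts agree and the any-cause shell rows do not fit the protocol's rule.

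If the related-only reading is followed, the result depends on attribution. The factor a_R/a_S is exact algebra; its size is not known. The range of 0.33 to 16 with no true effect rests on assumed shares of 10 to 80% and 5 to 30%. No single value in it, such as the ratio of 10 at 50% against 5%, should be read as the expected bias, because the documents give neither attribution shares nor incidence and do not show that attribution will differ by cohort. The reach is two targeted events.

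**What to change.** **Malignancy.** In SAP Table 5, delete the statement that all-cause malignancies are described but not compared. Use the DHR value malignant neoplasm, as listed in protocol Table 8, in place of neoplasm. State that all new malignancies are compared with IPTW, as the protocol has it, with related events shown as supplementary. Label the existing row in shell Tables 15 and 16 as any cause and add a treatment-connected row.

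**Thromboembolic events.** Amend protocol Table 8 and SAP Table 5 so that any-cause and related events are both analysed, matching the shells and the handling of severe liver disease and of adverse events leading to hospitalization or death.

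**Interpretation.** Keep the section 10.5 caution on all-cause results, and add that related-only results depend on the physician's attribution, including how unknown entries are handled.

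**Cost.** A few table-row edits, including one protocol row, before the SAP is finalised. No new data or models are needed. The small downside is that any-cause counts include background events unrelated to treatment.
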